Physical Activity in the Medical Workplace: A way to improve physical and mental well-being?

NCT02794727

04 April 2019

Title: Physical Activity in the Medical Workplace: A way to improve physical and mental well-being?**Abstract**

Many Americans do not meet the physical activity guidelines and the majority of Americans are overweight or obese. Decreased physical activity is not only associated with multiple chronic medical conditions, including obesity, but also with depressed mood, and other negative emotions. As many employed adults spend a great deal of time at work where we are predominantly sedentary, strategies to increase physical activity at work are being pursued to help improve the physical and mental health of Americans. This 17 week randomized controlled trial will investigate changes of occupational physical activity in three groups: those provided with a FitBit® but not able to monitor their activity level, and those provided with activity goals and individual physical activity challenges, and those who do not use a FitBit®. We hypothesize that providing awareness of occupational physical activity level as measured by an accelerometer (FitBit®) will increase occupational physical activity. In addition, we hypothesize that as measured by the SF-36® and perceived stress scale questionnaire measures of emotional health will also improve.

Specific Aims/Objectives

1. We hypothesize that utilizing a FitBit® to monitor activity level (i.e. Step count); will lead to increased occupational physical activity (OPA).

Background

Less than a third of American adults reach the CDC physical activity guidelines [2]. Many of our occupations are sedentary and lead to decreased time in physical activity [3, 4]. Being sedentary is associated with multiple adverse health outcomes, including obesity [5, 6]. In an effort to improve health, many workplaces and schools are attempting interventions to help increase occupational physical activity (OPA) [7].

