In addition to general health benefits, participation in regular physical activity has been associated with decreased risk of depressive symptoms [8]. A review of school and workplace interventions to increase physical activity found that after the intervention there were improvements in self-esteem, self-efficacy, satisfaction and commitment while there were decreases in anger, difficulty concentrating, fatigue, stress and feelings of sadness and depression [7]. A variety of interventions have been tried in numerous settings, many using self-report or questionnaires of physical activity [7, 9]. Interventions utilizing pedometers and providing activity goals have been successful at increasing OPA at a multi country university study [9]. Correlations with the improvement in OPA with markers of physical and mental well-being were not performed [9].

Our goal with this study is to further investigate the efficacy of workplace interventions to improve physical activity as measured by an accelerometer (FitBit®). The FitBit® has been previously validated as a reliable step counter [10]. Our workplace includes many different occupations and we will investigate if participant knowledge of OPA level leads to improved OPA levels. Further, if there is an increase in OPA, is this associated with weight loss and with decreased feelings of sadness and depressive symptoms.

Project Design/Methods**Study Subjects**

All employees within divisions of DOM will be eligible to participate in the present study. This will be a 17 week randomized controlled trial with a 4-week run-in phase, a 12 week randomized intervention phase, and a 1 week post intervention phase.

Inclusion criteria:

1. Be between 18 – 65 years of age
2. Be a Mayo Clinic employee at 0.75 FTE or more
3. Have not used an activity monitor within 2 weeks of study entry
4. Agrees not use any other activity monitor during study participation
5. Not be pregnant by subject self-report
6. Have a stable weight-defined as self-reported weight that has not changed more than 10% in the past 3 months
7. Not have any previous history of joint problems that limit free movement, as determined by the PI
8. Be able to participate fully in all aspects of the study
9. Have understood and signed study informed consent

Exclusion criteria:

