All eligible subjects will be invited to participate in 4-week run-in phase using the FitBit® while at work and be blinded to the FitBit® daily activity recording. This run-in phase will be used to collect baseline OPA data for each subject. During the run-in phase subjects will be provided with a FitBit® but will not be made aware of their OPA level. FitBit® accounts will be created and maintained by the study team. The FitBit® itself will have the displays covered so that it will not be available for the subject to read during the blinded phase(s). During this time subjects will be asked to wear their FitBit® while working and leave the FitBit® at their desk at the end of

each day. The FitBit® will be collected by study staff at the end of the subjects' workweek. During which time the coordinating staff will download the weekly data and recharge the devices. They will then return the devices to the subjects at the beginning of their work week. At the end of the 4-week run-in-phase (baseline) they will be randomized into one of the three 12 week intervention arms using a computer-driven random number generator created with the help of statistician. The groups to which they will be randomized will be:

1. **Group 1** (control group)- participants will be blinded to their OPA during the entire study (run-in and randomized intervention phases).

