2. **Group 2** (intervention group)- This group will be able to access their FitBit® activity data by viewing the display, therefore they will be unblinded during the randomized intervention phase (and blinded during the run-in phase). Participants will be given a specific OPA target based on the results from the run-in phase. The principal investigator or one of the co-investigators will meet with the participants randomized into this intervention group. The investigator will meet with subjects within 1 week of the study visit (baseline and week 6). Based on the physical activity tracked during the baseline period, instructions will be provided to increase the OPA by 5 % a week as determined by their average OPA at their last study visit. If at the post 6 week study visit their OPA remains <5000 steps per day, we will encourage the same 5% per week increase in OPA. Various methods such as taking steps as much possible prior to taking elevators, lunch time walks, walking breaks, and walking meeting of non-patient related topics will be suggested. The daily FitBit OPA activity will be downloaded weekly by the study staff and a print out of the weekly activity will be placed in the subjects study files for use by the investigators during these feedback sessions with the subject.
3. **Group 3** (no FitBit® Group) – No FitBit® during the 12 week randomized intervention phase.

As in the run-in phase, subjects will be asked to wear their FitBit® while working and leave the FitBit® at their desk at the end of each day. The FitBit® will be collected by study staff at the end of the subjects workweek. During which time the coordinating staff will download the weekly data and recharge the devices. They will then return the devices to the subjects at the beginning of their work week.

All subjects will be contacted for a final study visit via the telephone at 1 week post the randomized intervention.

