All data will be collected by the Study coordinator or by an online RedCap survey emailed to the subject. After consent and screening is completed, Perceived stress scale questionnaire and SF-36®, height, weight and InBody 770® scan will be collected, followed by providing the participant with his/her FitBit® for the run-in-phase. After the 4-week run-in-phase is completed, subjects will come in for randomization to one of the groups described above.

FitBit® devices will be collected on a weekly basis to download activity levels and charge the devices. A FitBit® account will be created for each study participant by the research coordinator to allow us to track activity level while keeping all participants blinded during the run-in-phase and group 1 blinded during the randomized intervention phase . FitBit® display will be hidden from the wearer for Group 1. For Group 2, The online program will allow us to limit the information the FitBit® wearers see so that the FitBit® can be specific to the goals set by the investigators. We will repeat the perceived stress scale questionnaire, SF-36® and InBody 770® after 6 weeks in the intervention phase and at week 12 which is the end of the randomized intervention phase.

One week after the completion of the study, we will complete one phone visit with each of the subjects.

Subjects must wear the FitBit® at work for a minimum of 48 days out of the possible 60 days during the randomization phase.

Data Handling

To ensure the confidentiality of the subjects participating in the present study; no names, social security numbers, hospital or clinic numbers will be included in the biostatistics databases. Names, addresses, telephone numbers, and any other information needed for recruitment, study involvement, and tracking will be obtained and maintained by the project personnel in a secured server with limited access. In addition, all study data (i.e. data collection forms as well as regulatory paperwork) will be maintained on a secure file server or in locked research data storage rooms to which only designated project staff will have access. All computer files and systems will be password protected and accessible by authorized personnel only. Data entry and transfer will be performed by the study staff after IRB approval.

Data Analysis

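### Occupational physical activity is handled as steps per day with no record of hours worn, so the plan cannot separate more stepping from longer wear in the unblinded Group 2

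*Combined protocol and SAP*

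**What the plan says.** All references are to the combined protocol and SAP.

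- **Outcome.** The single aim under Specific Aims/Objectives is that monitoring step count with the device raises OPA. The Group 2 description works in average daily steps: "instructions will be provided to increase the OPA by 5 % a week as determined by their average OPA at their last study visit", with a further rule that begins "If at the post 6 week study visit their OPA remains <5000 steps per day". Data Analysis specifies a t-test, or a rank-sum test if the data are skewed. It names no OPA summary, baseline adjustment or wear term.
- **Wear within the day.** Under Study Groups, "subjects will be asked to wear their FitBit® while working and leave the FitBit® at their desk at the end of each day". Staff collect the devices at the end of each work week to download and recharge them. The same arrangement applies in the run-in.
- **Wear across days.** Data Collection has the only quantified rule: "Subjects must wear the FitBit® at work for a minimum of 48 days out of the possible 60 days during the randomization phase". No such rule is stated for the 4-week run-in that supplies the baseline.
- **Difference between arms.** For Group 2, "This group will be able to access their FitBit® activity data by viewing the display". Group 2 also has a step target and meets an investigator, who reviews OPA against the goal after 6 weeks. Group 1 stays blinded throughout and is given no target. Group 3 has no device in the randomised phase, so OPA can be compared only between Groups 1 and 2.

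**The concern.** A daily step total is the stepping rate multiplied by the time the device is worn. A day worn for a few hours and a day worn for a full shift count equally towards 48 of 60. Group 2 can watch its total rise and knows it will be discussed. That gives it a reason to put the device on earlier, take it off later or avoid gaps. Group 1, with a hidden display and no target, has no matching reason.

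Any such difference would arise after allocation, so neither randomisation nor the blinded run-in would remove it. It would also point in the direction of the hypothesis. At stake is the interpretation of the one numbered aim: a Group 2 v Group 1 difference in steps per day could partly reflect wear, and the plan as written collects nothing that would show whether it did.

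**Working it through.** **Plan's own figures.** The only design calculation (Sample Size) concerns weight loss. A two-sided t-test with difference 2.5, SD 4.00, alpha 0.05 and 80% power gives 41.17, rounded up to 42 per group, as stated. It does not bear on OPA. The day rule is 48/60 = 80% of days (12 weeks × 5 days = 60) and sets no limit on hours within a day.

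**Model.** Steps per day = r × h, where r is steps per worn hour and h is hours worn. If r does not change and h rises by Δ, the apparent gain is Δ/h, while the true change in stepping rate is zero.

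**Inputs.** The documents give neither h nor Δ. Both are assumptions: h of 8 hours, with 6 hours as the lower end of a range, and Δ of 0.5 to 1 hour. For scale, the plan's 5000 steps a day is used.

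| Assumed h | Δ = 0.5 h | Δ = 1 h |
|---|---|---|
| 8 h | 0.5/8 = 6.25% (about 312 steps) | 1/8 = 12.5% (625 steps) |
| 6 h | 0.5/6 = 8.3% (about 417 steps) | 1/6 = 16.7% (about 833 steps) |

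**Compared with the coaching goal.** Five per cent a week for six weeks is 6 × 5% = 30% on a fixed base, or 1.05^6 − 1 = 34% compounded. At h = 8, one extra hour equals 12.5/34 to 12.5/30, about 37% to 42% of that goal. Half an hour equals 6.25/34 to 6.25/30, about 18% to 21%.

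**What cannot be computed.** The documents give no SD for OPA, so the chance that such a difference would reach p < 0.05 cannot be derived from them.

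**Check on a tempting correction.** Dividing by hours that contain steps looks natural but can reverse a real effect. Assume an 8-hour shift worn throughout, with 4000 steps in 6 of the hours: 4000/6 = 667 per stepping hour. Coaching then adds 500 real steps in the 2 hours that were still: 4500/8 = 563. True OPA rises by 500/4000 = 12.5%, while this measure falls by about 16%. Dividing by the whole worn span gives 4000/8 = 500 and 4500/8 = 562.5, a rise of 12.5%, which is correct.

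**The case against.** The case against runs as follows.

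1. **Wear is not left open.** Participants are told to wear the device at work and leave it at the desk, and staff collect it weekly. This stands in part: it limits evening and weekend wear in both device groups. But the desk rule is a request with no stated check, and neither measure governs hours worn within the workday.
2. **Steps per day is an inference.** This is correct. The 5000-step figure is a coaching threshold, and Data Analysis defines no OPA endpoint. No per-hour measure appears anywhere, however, so the gap remains.
3. **There is no evidence that wear will differ.** This also stands. A reader might infer that differential measurement error is established, or that a Group 2 gain would be an artefact. The documents support neither: they show an incentive that differs by arm and no means of checking its effect. Some extra lunchtime steps would be genuine, since lunch walks are among the suggestions made to Group 2.
4. **The illustration is generous.** If a shift lasts 8 hours and is worn throughout, wear within it cannot lengthen. The extra time needs a longer day on site or a starting wear below the full shift. This is fair, and is why the figures are a range under assumptions.
5. **Shift length.** A reader might take the entry criterion "Be a Mayo Clinic employee at 0.75 FTE or more" as a further source of bias. It is not: working hours are a baseline characteristic that randomisation balances on average, so they add noise and no bias between arms.
6. **This is a pilot sized on weight.** True, and it limits the severity. It does not make the OPA comparison interpretable.

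**Conclusion.** The concern holds as a risk of unknown size. Following the plan as written, a Group 2 v Group 1 difference in daily steps cannot be divided into more stepping and longer wear within the workday. With an assumed 8-hour worn day and constant stepping rate, 0.5 to 1 extra hour a day gives an apparent gain of about 6% to 12.5%. That is not negligible beside a six-week goal of 30% to 34%, but it is an illustration and not an estimate of bias. The conclusion rests on reading OPA as average steps per day and on the incentive to extend wear being present only in Group 2. The plan should be changed, but the trial can proceed.

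**What to change.** 1. **Define the measure.** Keep mean steps per worn workday as the OPA measure for Group 2 v Group 1, and state what counts as a worn workday in both the run-in and the randomised phase.
2. **Adjust for the run-in value.** Use ANCOVA in place of the unadjusted t-test. The run-in data are already collected, and this also absorbs stable differences in shift length. It does not remove a change in wear after randomisation.
3. **Describe wear.** Where the study-controlled accounts allow a time-stamped export, derive daily wear by a rule that does not treat still hours as non-wear, for example the time from first to last recorded activity. Report it by arm for the run-in and intervention phases.
4. **Add a sensitivity analysis.** Limit days to a common minimum wear, or account for wear duration. If wear differs by arm, qualify the OPA conclusion.
5. **If only daily totals can be exported,** state that differential wear cannot be excluded.

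Three alternatives should not be used. A denominator of hours with steps can turn a true gain negative, as shown in the working. A rule that steps per day and steps per such hour must both show a gain would then reject a real effect. Scheduled hours recorded at enrolment are fixed before allocation and cannot reveal a later change in wear.

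The cost is extra data processing and possibly a different export, with no new visits or participants. The wear estimate will be imperfect; a first-to-last span, for instance, misses removal in the middle of the day. It is also measured after randomisation, so it can support a sensitivity analysis only.

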1. Have a known history of any condition or factor judged by the investigator to preclude participation in the study or which might hinder adherence or skew data collection – such as a position where they predominantly provide transport as part of their job

Study Groups

We propose to recruit, consent and screen 270 subjects through IRB approved contact materials such as e-mail, phone call, flyers, and classified advertisements in order to randomize 135 to study. All subjects who respond will be pre-screened for inclusion and exclusion criteria via a telephone pre-screen. Those who meet criteria will be invited to a consent visit followed by a study screening visit. After consent and screening has taken place, subjects who meet all study entry criteria will be invited to participate in the study.

When a subject is found to be eligible for the study, they will be asked by the study staff to create a google email which will be used by the study to download their weekly fitbit data. Subjects will not have access to this google email password since they need to remain blinded to the fitbit data during the trial, but the email and password will be returned to them at the end of the study and they will be shown how to change their password so that it can remain confidential. They will also be informed that they will be able to keep the fitbit assigned to them once they complete all 17 weeks of the study. The google email is used by the study staff to download their weekly data in an online account and this is the outcome data needed for the study.

The first 20 subjects enrolled in the study will be asked to participate in an additional validation phase. For this validation phase of the subject will be asked to wear a FitBit® on both wrists and walk on a treadmill, located in the DAHLC, while the study coordinator records their steps manually using a clicking device. The subject will be asked to walk for 5 minutes at 0.9 MPH, followed by 5 minutes at 3.0 MPH and 5 minutes at 4.0 MPH. They will then be asked to continue on with the blinded run-in phase.

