At baseline, and 6 weeks after they start the randomization intervention and at the end of the randomization phase (12 weeks) all study participants will be asked to complete the perceived stress scale, the SF 36 scale and be measured by the InBody 770®. In addition, subjects in group 2 will meet with one of the study investigators. OPA during the first 6 weeks of intervention period would be reviewed. For participants who have met the goal OPA, only feedback to continue the OPA would be provided. For participants who have not met the goal OPA, further instructions will be provided to improve the OPA.

Sample Size

A sample size of 42 in each group will have 80% power to detect a difference in the mean of 2.5% weight loss difference between a Group 1 and Group 2, or Group 1 and Group 3, or Group 2 and Group 3 assuming that the common standard deviation is 4.00 using a two group t-test with a 0.050 two sided significance level as shown below. Adding a control will not change the sample size required in each group since, there will only be a comparison between only two groups at a time.

Two group t-test of equal means (equal n's)				
Column	1	2	3	4
Test significance level, α	0.050	0.050	0.050	0.050
1 or 2 sided test?	2	2	2	1
Group 1 mean, μ_1	2.500	2.500	2.500	2.500
Group 2 mean, μ_2	5.000	5.000	5.000	5.000
Difference in means, $\mu_1 - \mu_2$	-2.500	-2.500	-2.500	-2.500
Common standard deviation, σ	6.000	5.000	4.000	4.000
Effect size, $\delta = \mu_1 - \mu_2 / \sigma$	0.417	0.500	0.625	0.625
Power (%)	80	80	80	80
n per group	92	64	42	33

From the research studies conducted at Mayo Clinic in the past, there is a 6 – 7% drop out rate in the recruitment. To account for this drop-out rate, we propose to include 45 subjects in each arm of the study. We acknowledge that achieving a 2.5 % change in body weight might not be clinically feasible. We propose to run this study as pilot study to estimate the amount of weight loss, change in body fat percentage and improvement in satisfaction level. We propose to run a larger randomized controlled study using this as preliminary data.

Data Collection

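### The only stated power is for a 2.5% weight-loss difference, while the only Specific Aim is occupational physical activity (OPA), for which no power, analysed variable or contrast is stated

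*Combined protocol and SAP*

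**What the plan says.** **Aim.** Specific Aims/Objectives has one numbered item, the hypothesis that "utilizing a FitBit® to monitor activity level (i.e. Step count); will lead to increased occupational physical activity (OPA". The Abstract says the trial "will investigate changes of occupational physical activity in three groups" and adds a hypothesis on SF-36 and perceived stress. Study Groups says of the weekly FitBit download that "this is the outcome data needed for the study".

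**Power.** The calculation reads: "A sample size of 42 in each group will have 80% power to detect a difference in the mean of 2.5% weight loss difference", for any of the three pairwise contrasts, with a common SD of 4.00 and a two-sided 0.05 t-test. The allowance for 6–7% dropout follows: "To account for this drop-out rate, we propose to include 45 subjects in each arm of the study". The section then says: "We acknowledge that achieving a 2.5 % change in body weight might not be clinically feasible". It calls the study a pilot to estimate weight loss, body-fat change and satisfaction. OPA is not in that list.

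**OPA measurement.** All subjects wear the device before randomization: "This run-in phase will be used to collect baseline OPA data for each subject". Group 3 then has "No FitBit® during the 12 week randomized intervention phase". Data Collection requires at least 48 of 60 days of wear in the randomized phase, without excepting Group 3.

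**Analysis.** Data Analysis plans a t-test between groups, or a Wilcoxon rank-sum test if data are skewed, at two-sided p < 0.05. It names no primary endpoint, time window or contrast, and does not say whether final values or changes are compared.

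**The concern.** A reader who sees 80% power will take it to apply to the question the trial asks. Here it applies to weight, which is in no numbered aim. The Background raises weight loss only as a possible correlate of a rise in OPA. For OPA itself the documents give no between-group difference, no SD and no power. The 5%-per-week figure in Study Groups is a coaching target for Group 2, not a difference the trial is sized to detect.

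The ranking of weight and OPA is also open. The aim points to one, Sample Size to the other, and one significance rule covers every comparison. The step summary and its time window are undefined, so they could be chosen after the data are seen. Finally, the Abstract promises OPA changes in three groups, which the design cannot deliver after randomization.

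**Working it through.** **1. The plan's own figure.** Inputs from Sample Size: difference 2.5, SD 4.00, two-sided 0.05, 80% power. Effect size = 2.5/4 = 0.625. The noncentral t gives n = 41.17, so 42 per group; power at 42 is 80.8%. The other columns also reproduce: 92 (SD 6), 64 (SD 5) and 33 (SD 4, one-sided). Dropout: 45 × 0.94 = 42.3 and 45 × 0.93 = 41.85, so 45 per arm leaves about 42. There is no arithmetic error.

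**2. Which OPA contrasts exist.** Groups 1 and 2 wear the device during the 12 weeks; Group 3 does not.

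- Group 2 v Group 1: available.
- Group 1 v Group 3: not available.
- Group 2 v Group 3: not available.

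One of three remains, and it is the one the aim needs.

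**3. What 42 per group detects for OPA.** The documents give no SD for steps, so results are in SD units. Let r be the correlation between run-in and intervention OPA. No value is given; 0.5, 0.7 and 0.8 are assumed, with equal variances at the two times. Two-sided 0.05, 80% power.

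- Final-value t-test (82 df): 0.619 SD.
- Change-score t-test: 0.619 × √(2(1 − r)), with factors 1.000, 0.775, 0.632.
- ANCOVA on run-in OPA (2 × 42 − 3 = 81 df): 0.619 × √(1 − r²), with factors 0.866, 0.714, 0.600.

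| Analysis | r = 0.5 | r = 0.7 | r = 0.8 |
|---|---|---|---|
| Final value | 0.62 | 0.62 | 0.62 |
| Change score | 0.62 | 0.48 | 0.39 |
| ANCOVA | 0.54 | 0.44 | 0.37 |

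**4. Equivalent sample size of ANCOVA with 42 per group.**

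- Against final values: 42/(1 − r²) = 56.0, 82.4, 116.7.
- Against change scores: 42 × 2(1 − r)/(1 − r²) = 84/(1 + r) = 56.0, 49.4, 46.7.

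The gain depends heavily on which t-test the plan intends, and the plan does not say.

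**5. Why SD units are not enough.** At an assumed SD of 1000 to 3000 steps a day, 0.62 SD is 0.62 × 1000 = 620 to 0.62 × 3000 = 1860 steps a day. Without an SD, nobody can judge whether the detectable difference is plausible.

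**6. Precision for weight.** 95% CI half-width with 42 per group and SD 4: t(0.975, 82 df) × 4 × √(2/42) = 1.989 × 4 × 0.2182 = 1.74 percentage points.

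**The case against.** **The study is a pilot.** Sample Size says so, says the results will feed a larger trial, and concedes that 2.5% may be out of reach. That lowers the need for formal power. It does not remove the mismatch: the plan still claims 80% power, still tests at p < 0.05, and leaves OPA out of what the pilot is to estimate.

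**OPA in Group 2 v Group 1 is implied as primary.** There is one numbered aim, the FitBit data are called the outcome data, and the two groups are labelled control and intervention. This largely stands for the endpoint concept and the contrast. The summary measure, the time window and the ranking against weight remain open.

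**An effect size of 0.625 carries over to any endpoint.** True in SD units only.

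Three stronger readings are tempting, and the documents do not support them.

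- *OPA is underpowered.* At 42 per group a final-value t-test has 62% power for an assumed 0.5 SD and 27% for 0.3 SD, but the documents give no expected difference or SD with which to choose among such values.
- *The planned test ignores the run-in.* Data Analysis does not define the analysed variable. The Abstract speaks of changes, the run-in is collected as baseline, and weight loss is itself a change. A change-score t-test, which already uses the run-in, is plausible. The 82 and 117 equivalents at r = 0.7 and 0.8 therefore cannot be claimed as the gain over the plan; it may be only 49 and 47.
- *The wear-day rule will cut the evaluable number below 42.* Data Collection states the requirement but no consequence. Exclusion can be inferred only by joining it to the evaluability sentence in Data Analysis, and no expected non-compliance is given.

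**Conclusion.** The concern holds as a mismatch between aim and sample size, together with an undefined main analysis. The 42 per group is correctly computed, for weight only. With 42 evaluable per group, the OPA comparison has 80% power for 0.62 SD before adjustment. With ANCOVA this falls to 0.54, 0.44 or 0.37 SD, under equal variances and assumed r of 0.5, 0.7 or 0.8. The improvement over the plan ranges from large (if final values were intended) to modest (if changes were intended and r is 0.7 or 0.8). It comes without extra subjects in either case. The Abstract's three-group OPA comparison is not possible after randomization. The point should be fixed, but it does not undermine the choice of N.

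**What to change.** 1. **Primary analysis.** Name mean steps per worn workday over the 12-week phase, Group 2 v Group 1, by ANCOVA adjusted for run-in OPA. Keep the t-test or Wilcoxon test as a sensitivity analysis and say which variable it compares. If the sponsor prefers weight as primary, rewrite the aim to match.
2. **Sample Size.** State that the 80% applies to weight only, and that 42 evaluable per group gives 80% power for an OPA difference of 0.62 SD before adjustment, smaller with run-in adjustment. The sponsor should add the step difference of interest. The blinded run-in SD can convert SD units to steps, as an approximate guide only: it comes from four weeks before intervention, not from a 12-week mean under coaching. Do not put assumed evaluable numbers below 42 into the protocol.
3. **Pilot sentence.** Add OPA to the quantities to be estimated, and report weight differences with 95% CIs (half-width about 1.7 points at SD 4).
4. **Abstract and wear rule.** Say that post-randomization OPA is compared in Groups 1 and 2 only, with weight, body composition, stress and SF-36 compared in all three. Reconcile the wear-day requirement in Data Collection with Group 3 having no device.

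Cost: rewording and one covariate already collected. N stays at 45 per arm. The weight power is no longer the headline, and the adjusted OPA figure depends on a correlation that is not yet known.
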